Protocol for Almond Butter and Fasting Glucose Study

Identifiers: NCT03826472

Unique Protocol ID: PKE AlmondButter

Brief Title: Almond Butter and Fasting Glucose

Updated May 2, 2022

Protocol for Almond Butter and Fasting Glucose Study

Inclusion Criteria

- Individuals 18 to 75 years of age
- Individuals with diagnosed type 2 diabetes
- HgbA1c: <9%
- Not on insulin therapy
- On stable doses of oral antihyperglycemic agent (no dose change for 6 months) or no oral antihyperglycemic agents
- Willing and able to adhere to study protocol

Exclusion Criteria

- Individuals with type 1 diabetes, cardiovascular disease, kidney disease, liver disease, cancer or inflammatory conditions (e.g. GI disorders, rheumatoid arthritis)
- Women who are pregnant, breastfeeding, or have been pregnant within the last 6 months or breastfeeding within the last 6 weeks
- Individuals who smoke or use tobacco products
- Use of insulin therapy or sulfonylurea medications
- Almond allergy
- Allergy to Dexcom CGM adhesive

Recruitment

Advertisements will be placed in campus buildings and facilities as well as the surrounding area (gyms, churches, supermarkets, coffee shops etc.) to identify potential subjects residing in and around the State College area. We will also provide flyers to local physician offices and recruit through our Facebook page and department website.

Study staff will contact those individuals who have responded to ads (email, newspaper, website, fliers) and have left their name and phone numbers on the recruiting line or email.

Recruitment flyers will be posted in local physician offices. Cardstock fliers may also be distributed to patients or displayed in the waiting room of the office. Websites (<http://clinicaltrials.gov/>, <https://studyfinder.psu.edu/>, Facebook, Craig's List), PSU listserv (Health and Human Development Dept listserv; Food Science listserv; post-doc etc.) will also be utilized. Participants will be asked to complete a brief phone screening to confirm eligibility.

Consent Process and Documentation

Once interested participants have contacted study staff and have undergone a phone screening, an appointment will be set at the General Clinical Research

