Center (GCRC) where study staff will review the consent documents with participants. At this appointment, before any procedures take place, potential participants will be given the informed consent document. Following standard protocol procedure, a trained staff person will review the information in detail, make sure the individual understands the study and answers any questions they may have. If the participant is still interested in enrolling in the study, both the participant and the staff member will sign and date the document. A copy of the signed document will be provided to the participant prior to leaving the screening appointment. If consent is obtained, the study protocol will be reviewed, the Dexcom monitor will be placed, and the subject will begin the study that day. Subjects will be made aware that their participation in this study is voluntary, they may drop out of the study at any time, and that there is no penalty for not participating. Consent will be confirmed in writing.

Protocol

After completion of the phone screening, an appointment will be set for a baseline visit at the GCRC to obtain informed consent and place the continuous glucose monitor. If the participant consents to the research, the researcher will play a brief video detailing how to use place a Dexcom Continuous Glucose Monitor (CGM), and participants will then place the monitor on themselves, under the supervision of study staff. Participants will be taught to use the CGM properly and will wear it for 3-7 days. The CGM can be worn for up to 7 days, according to manufacturers' instruction, but in some individuals, the adhesive does not stay in place for the full week. We will plan for study participants to wear the CGM for 7 days, but we will accept a minimum of 3 days of data.

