The Continuous Glucose Monitor data receiver will be set to blinded mode and participants will not be able to see their glucose data for the duration of participation (they will still monitor their blood glucose as instructed by their physician, they just will not be able to see it on the CGM). Participants will wear the CGM for 3-7 days, return to the clinic for removal and replacement, and then begin the second study period. They will also be provided with the study food, almond butter, and be asked to consume the almond butter that we provide to them as a bedtime snack for the 3-7 nights of the study. The order of their treatment (control then almond butter or almond butter then control) will be randomly assigned. We will also ask participants to keep a record of what they eat for dinner, what time they eat breakfast, lunch and snacks, and any changes in medication or physical activity on those days. Participants will receive individual packets of 2 tbsp of natural almond butter and be given instructions to eat the almond butter as an evening snack, or to eat nothing after dinner during the no-snack control period. Blood glucose levels will be measured using continuous glucose monitoring (CGM), which will be provided free of charge to participants through a donation from Dexcom. At Visit 3, participants will have the CGM removed and will receive a printout of their CGM data when they return the Dexcom equipment to the office.

Visit 1

The study will be explained, questions will be answered and consent forms will be reviewed and signed. Participants providing consent will watch a brief video on use and placement of CGM, and then place their CGM in the office, supervised by study staff. They will be taught to use the CGM, be provided with the study food, food record sheets and randomized. They will also have an appointment set for 6-14 days later.

Visit 2

At the second visit, participants will remove and replace their CGM monitor. They will be reminded of all data entry requests.

Visit 3

At the third visit, participants will return their CGM equipment and their data will be downloaded. They will receive their CGM data and be entered into a drawing to win a gift card for their participation. They will receive the \$100 incentive for participation approximately two weeks later.

Duration of Participation

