Participants will first complete a phone screening. If they are deemed eligible, they will participate in the study for 2 weeks, including 3 visits to the clinic. Visit 1 lasts approximately 1 hour, visits 2 and 3 last approximately 15 minutes.

Intervention Food (Almond Butter)

The almond butter will be packaged into 7 single serving containers to be consumed during the intervention week. Participants will be given individual containers as dictated by the study design, 1 per day, for the duration of the intervention, at their first visit. There are no special requirements for storage by the participants.

Subject Numbers and Statistical Plan

Ten participants were recruited for this study. All data collected, including CGM and dietary data, will be identified with a code. None of the collected data will include patient identifiers. Only the PI and study personnel will have access to study data. Linear mixed effect models in R statistical software (The R Project for Statistical Computing) will be used to analyze the data.

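### Does a plan that names only linear mixed models leave this ten-person crossover analysis too open to stand?

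*Combined protocol and SAP*

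**What the plan says.** The section Subject Numbers and Statistical Plan holds the only analysis statement: "Linear mixed effect models in R statistical software (The R Project for Statistical Computing) will be used to analyze the data". The same paragraph opens with "Ten participants were recruited for this study". It gives no significance level, power, effect size or variance.

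The outcome has to be inferred. The title block reads "Brief Title: Almond Butter and Fasting Glucose", and the Protocol section says that glucose is measured by CGM. No time window or nightly summary is given.

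The design is in the Protocol section. It is a two-period crossover: "The order of their treatment (control then almond butter or almond butter then control) will be randomly assigned". Each period has its own sensor placement: "Participants will wear the CGM for 3-7 days, return to the clinic for removal and replacement, and then begin the second study period". The amount of data per period can vary: "We will plan for study participants to wear the CGM for 7 days, but we will accept a minimum of 3 days of data".

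**The concern.** Condition varies between a participant's two periods, not from night to night. Nights in the same period share a condition and a sensor placement, and may share diet and activity that week. Ten participants therefore supply ten within-person contrasts, however many nights are recorded.

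The sentence in the plan covers several different fits. One mean per participant-period leaves 9 residual df, or 8 with a period term. A nightly model with only a participant intercept leaves 129 at 7 nights. If nights within a period are correlated, the nightly fit overstates the information and its interval is too narrow. Two analysts could follow the sentence, analyse the same data and disagree on significance.

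Timing adds to the unease. Recruitment is in the past tense and the analysis in the future, and nothing shows when the model was settled relative to sight of the CGM data.

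**Working it through.** There is no stated figure to reproduce, so the check asks how far fits that obey the sentence can differ.

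**Inputs from the document.** n = 10 participants, 2 periods, m = 7 nights planned and 3 as the minimum.

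**Assumed.** Orders split 5:5, all ten complete both periods, two-sided 95% intervals. Let rho be the correlation of nights within a period, net of the participant's own level. The document gives no value; 0 to 0.3 is used. Night-level variance is set to 1.

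**Degrees of freedom.** Nightly fit with a participant intercept: 2nm − n − 1 = 140 − 11 = 129 at 7 nights and 60 − 11 = 49 at 3. Period means: 20 − 10 − 1 = 9, or 8 with a period term.

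**True against reported standard error of the nightly fit.** A participant-period mean has variance v = rho + (1 − rho)/m, net of the participant's level. The nightly fit uses s²/m in its place, where s² = [9(1 − rho + m·rho) + 20(m − 1)(1 − rho)]/(20m − 11). At m = 7 and rho = 0.3:

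- v = 0.3 + 0.1 = 0.4
- s² = (9 × 2.8 + 120 × 0.7)/129 = 109.2/129 = 0.847
- SE ratio = √(0.4/(0.847/7)) = 1.82

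At rho = 0 the ratio is exactly 1.

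**Mean 95% half-widths, m = 7.** For period-adjusted means the half-width is t₈ × 0.969 × √(2v/10), where 0.969 is the mean of √(χ²₈/8). For the nightly fit it is close to t₁₂₉ × √(2s²/70).

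- rho = 0: 2.306 × 0.969 × 0.169 = 0.378 against 1.979 × 0.169 = 0.334, a ratio of 1.13
- rho = 0.3: 2.306 × 0.969 × 0.283 = 0.632 against 1.979 × 0.156 = 0.308, a ratio of about 2.06

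**Simulation with no treatment effect, 20,000 replicates per cell, rho = 0, 0.05, 0.1, 0.2, 0.3**

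| Quantity | 7 nights | 3 nights |
|---|---|---|
| Mean width, period-adjusted means over nightly fit | 1.13, 1.31, 1.47, 1.78, 2.06 | 1.12 to 1.52 |
| Type I error, nightly fit | 5, 9, 13, 21, 28% | 5, 6, 8, 11, 15% |
| At least one of four fits gives p < 0.05 | 7.3, 10.4, 13.8, 21.3, 28.5% | 7.6, 8.0, 9.6, 12.5, 15.5% |
| Either period-means fit gives p < 0.05 | 5.5 to 6.0% | 5.5 to 6.0% |

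The four fits are nightly values or period means, each with or without a period term, and all with a participant intercept.

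**Where the spread comes from.** At rho = 0.3 and 7 nights, the 28.5% chance that some fit rejects is essentially the nightly fit's own 28%. If only the two period-means fits are considered, the chance is at most 6.0%. With no period effect, adding a period term to the means changes mean width by about 1.5%.

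The width ratios are also ratios of averages. In single datasets at 7 nights, the 10th to 90th percentile range is 0.78 to 1.50 at rho = 0 and 1.48 to 2.59 at rho = 0.3. At rho = 0 the period-means interval is the narrower one in about a third of datasets.

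**Period term.** A 6:4 split leaves (6 − 4)/10 = 20% of any period effect in an unadjusted difference, and 7:3 leaves 40%. Under simple randomisation (an assumption, since the method is not stated) P(not 5:5) = 1 − 252/1024 = 75%, and P(7:3 or worse) = 352/1024 = 34%. With a 5:5 split there is no bias. A period effect of 1 SD of the paired difference would then cut power for a 1 SD treatment effect from 79% (adjusted) to 48% (unadjusted). With no period effect, leaving the term out narrows the interval slightly. The plan is silent on the term; it does not exclude it.

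**The case for a change.** The strongest case for acting is that the gap is real and nothing elsewhere fills it. Nothing in the section is marked as removed. Even without a variance assumption, the choice of reference distribution moves a period-means interval by 2.262/1.960 = 1.15 times (9 df against normal) or 2.306/1.960 = 1.18 times (8 df). Raw CGM readings treated as independent would be worse still: with an assumed 12 to 36 readings per night and within-night correlation of 0.3 to 0.8, √(1 + (k − 1)·correlation) runs from 2.1 to 5.4 on the standard error. One paragraph of text would close all this at no cost in data.

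Much of that stands as description. The document does not fix a single result, and a reader cannot tell from it when the model was chosen. But the difference in tense does not show that the choice stayed open after data were seen. The large figures also all belong to fits that ignore the crossover structure. The plan names neither, and it chose a model class whose purpose is to represent grouped data. Outcome, period term and df are real omissions, but they are not what produces the 2.06 or the 28%.

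**Conclusion.** No change follows. The plan states no wrong rule or number; it names a suitable class of model and leaves the specification to the analyst. Two ordinary readings are sound for this design: one mean per participant-period, or nightly values with intercepts for participant and for participant within period. Either one respects the level at which condition is assigned and removes the problem. The period-adjusted means hold their error at about 5% at every rho examined. Writing one of these into the text would spell out an instance of what the plan already names.

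The damage of up to 28% type I error and a 2.06-fold difference in mean width needs three things together: all 7 nights, rho near 0.3, and an analyst who omits the participant-by-period level. At rho = 0 the nightly fit has correct size, and the mean width difference is 1.13 times. The rho range is assumed, and the calculations take ten completers with equal orders. What remains is a matter for reading the results: a report of this trial should be checked for how fasting glucose was defined and whether the df reflect ten participants.

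### Does the plan need to change because fasting glucose appears only in the titles and is never defined as the response of the mixed model?

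*Combined protocol and SAP*

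**What the plan says.** The title lines name the subject of the study, for example "Brief Title: Almond Butter and Fasting Glucose". The word fasting occurs three times, each time in a title, and there is no objectives or endpoints section.

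The Protocol section says "Blood glucose levels will be measured using continuous glucose monitoring (CGM". Participants are asked to "consume the almond butter that we provide to them as a bedtime snack for the 3-7 nights of the study", and a few sentences later to "eat the almond butter as an evening snack, or to eat nothing after dinner during the no-snack control period". They also "keep a record of what they eat for dinner, what time they eat breakfast, lunch and snacks". Seven days of CGM wear are planned, but "we will accept a minimum of 3 days of data". Under Visit 3, "participants will return their CGM equipment and their data will be downloaded".

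The only statement of method is that "Linear mixed effect models in R statistical software (The R Project for Statistical Computing) will be used to analyze the data". It gives no response variable, time window, rule for combining days, significance level or number of tests.

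**The concern.** A mixed model needs a response, and a CGM trace does not supply one unaided. It can be reduced to a last reading before breakfast, a short pre-breakfast mean, a fixed early-morning window, an overnight mean or a 24-hour mean. These are not interchangeable here. Only the almond butter condition includes food after dinner, so an overnight mean can take in part of the response to the snack in that condition alone, while a pre-breakfast value largely avoids it. The snack has no clock time and is described both as a bedtime and as an evening snack, so the overlap is not fixed by design.

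Timing adds to the worry. The plan reports in the past tense that ten participants were recruited, and data are downloaded as each participant finishes. If the summary were chosen after the two conditions had been compared, a nominal significance level would no longer describe the test.

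**Working it through.** The plan has no figure of its own to reproduce: the sample size of 10 comes without a significance level, power, effect or standard deviation. The check is therefore a reading of the text, followed by three illustrations on stated assumptions.

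**1. What is open and what is settled.**

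| Element | Where | Status |
|---|---|---|
| Quantity of interest | Titles | Fasting glucose, named |
| Instrument | Protocol | CGM |
| Contrast | Protocol | Late snack versus nothing after dinner, randomised order |
| Data needed to place a fasting window | Protocol | Breakfast times requested |
| Window on the trace | none | Open |
| From 3–7 days to analysed values | none | Open |
| Link from fasting glucose to the model | Titles only | Implied |

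The operational definition is missing; the target itself is named.

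**2. Number of responses.** Assume that all 10 complete both periods, that the three-day minimum applies to each period, and that each accepted day gives one morning. One value per morning then gives 10 × 2 × 3 = 60 to 10 × 2 × 7 = 140 values, a repeated-measures layout that suits a mixed model.

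**3. Error rate if the summary were picked for significance.** Assumptions, none from the documents: no true effect, 10 paired differences, a paired t-test in place of the mixed model, two-sided 5% level, and any significant summary reported. Proportion of 200,000 simulated trials with at least one |t| above t(0.975, 9):

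| Correlation | 2 summaries | 3 summaries |
|---|---|---|
| 0.5 | 9.2% | 12.7% |
| 0.7 | 8.5% | 11.4% |
| 0.8 | 8.1% | 10.3% |
| 0.9 | 7.2% | 8.9% |
| 1.0 | 5.0% | 5.0% |

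The upper limits, for independent summaries, are 1 − 0.95² = 9.8% and 1 − 0.95³ = 14.3%. With a single summary fixed first, the rate is 5%.

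**4. Does the choice of window matter?** Assume that the snack response rises linearly to 10 mg/dL at 1 hour and falls linearly to zero at h hours. If midnight comes m hours after the snack, with 1 ≤ m < h, the level at midnight is 10(h − m)/(h − 1). The contribution to a 00:00–06:00 mean is half that level times (h − m), divided by 6.

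- 20:30 snack (m = 3.5): 0 for h = 3; for h = 4, 0.5 × 0.5 × 1.67 / 6 = 0.07 mg/dL.
- 22:00 snack (m = 2): 0.5 × 1 × 5 / 6 = 0.42 for h = 3; 0.5 × 2 × 6.67 / 6 = 1.11 for h = 4.
- 23:00 snack (m = 1): 0.5 × 2 × 10 / 6 = 1.67 for h = 3; 0.5 × 3 × 10 / 6 = 2.50 for h = 4.

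Under the same shape, even the 23:00 snack with h = 4 has returned to zero by 03:00. A pre-breakfast or early-morning window starting after 03:00 carries none of it. The windows that differ materially are those that include glucose soon after eating, which the word fasting already argues against.

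**5. A more detailed rule has its own cost.** Suppose a missing breakfast time were replaced by the participant's earliest recorded one. With n other recorded and exchangeable mornings, the chance that the true breakfast was earlier still is 1/(n + 1). With 6 to 14 mornings in total, n is 5 to 13, giving 1/6 = 17% to 1/14 = 7%. If breakfast shifts by one standard deviation between conditions (an assumption; simulated normal times), the chance is about 12–28% in the earlier-breakfast condition and 2–6% in the other. The error would then differ between the conditions being compared.

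**The case for a change.** The strongest case for a change is that a title is not an outcome definition. Two analysts who follow this text faithfully could model a single pre-breakfast reading and a fixed-clock mean, and breakfast times are collected without being tied to anything. With ten participants and one sentence of analysis, a few added lines would cost almost nothing and need no new data.

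The factual part stands: the text does not define the window, the handling of days or the response. The inference to harm is weaker. It needs an analyst who compares several summaries and reports the favourable one, and the documents give no sign of that. It also presumes one confirmatory test at a set level, whereas the plan speaks of models in the plural and sets no level. Added text would count as pre-specification only if no comparison by condition had yet been seen, which the documents do not settle. Nor do they support one window over another, so any particular choice, such as 30 minutes before breakfast, would be a preference and would correct no stated method.

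**Conclusion.** No change to the plan follows. The omission is real, but it is missing detail that a competent analyst fills sensibly: the titles give fasting glucose, the control condition excludes food after dinner, and breakfast times allow a pre-breakfast or early-morning value for each morning. No rule or figure in the plan is wrong.

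Its size cannot be derived from the documents. The inflation to roughly 7–13% holds only under selective reporting of two or three correlated summaries at an assumed 5% level, and it disappears if one summary is fixed first or if the summaries agree perfectly. The post-snack contribution of 0 to 2.50 mg/dL per 10 mg/dL of peak applies to an overnight mean with an assumed response shape, not to a value taken shortly before breakfast. A reader of the results should check which window was used. The conclusion rests on the analyst taking the title at its word; evidence that the summary was chosen after the conditions were compared would alter it, and the documents contain none.
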